Following islet transplantation, the islets must acutely survive the stress of the procedure, and then they must engraft in the liver and establish a vascular supply. The greater the functional islet mass engrafted, the lower the risk of post-operative diabetes (6-10). Preventing early post-operative hyperglycemia reduces but does not prevent beta cell apoptosis. Even under conditions of adequate glycemic control, beta cell apoptosis is common during the first month post-transplant (11, 12) and is upregulated in the presence of inflammatory cytokines such as TNF- α . It has been estimated that more than half of the islet mass may be lost in the early post-transplant period (13). Thus, a **major contributor to islet loss** is the inflammatory damage sustained by the transplanted islets in the early post-transplant period; this in turn adversely impact long-term diabetes outcomes. **We propose to directly target this destructive process.**

engraft in the liver and establish a vascular supply. The greater the functional islet mass engrafted, the lower the risk of post-operative diabetes (6-10). Preventing early post-operative hyperglycemia reduces but does not prevent beta cell apoptosis. Even under conditions of adequate glycemic control, beta cell apoptosis is common during the first month post-transplant (11, 12) and is upregulated in the presence of inflammatory cytokines such as TNF- α . It has been estimated that more than half of the islet mass may be lost in the early post-transplant period (13). Thus, a **major contributor to islet loss** is the inflammatory damage sustained by the transplanted islets in the early post-transplant period; this in turn adversely impact long-term diabetes outcomes. **We propose to directly target this destructive process.**

Dramatic increases in beta cell apoptosis relative to that present in the native pancreas are observed *in vitro* in human islets and *in vivo* in animal models after islet isolation, increasing over the first 10 days post-transplant (12, 14), and worsened in the presence of inflammatory cytokines, such as TNF α (15). *In vitro* exposure of islets to TNF α alone or with IL-1 induces beta cell apoptosis (15). Expression of damaging inflammatory cytokines has been documented both in islet graft (16), and in total pancreatectomy islet autotransplant (TPIAT) recipients,

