The first hurdle to a successful islet transplant is the number of islets available, and thus the transplanted islet mass is an important predictor of subsequent diabetes risk (7-9, 21). However significant variability in diabetes outcomes is seen for any given transplanted islet mass. Approximately 70% of IAT recipients with >5000 islet equivalents (IEQ)/kilogram body weight transplanted will achieve insulin independence, while 30% never come off insulin despite the large number of islets infused. In contrast, nearly 10% of those patients with a very low islet mass (<2500 IEQ/kg) will maintain insulin independence, sometimes for years (7). This variability can largely be explained by the difference between the *transplanted* islet mass and the *engrafted* islet mass. Beta cell apoptosis and loss occurs in the immediate post-operative period due to the stress of the procedure and transplant environment. High levels of beta cell apoptosis are observed, particularly in the 7 days after surgery, with apoptosis observed even at 30 days (11, 12). It has been estimated that more than half of the islet mass may be lost in this early post-transplant period in islet transplant recipients (13). The innate inflammatory response, triggered by islet infusion, hypoxia, and hyperglycemic stress, is an important contributor to beta cell loss. In allograft transplant, successful engraftment of transplanted islets, as demonstrated by functional testing at 3 months, is strongly predictive of diabetes remission at 1 year, even more so than the initial number of islets transplanted (22). Thus, this is a critical early window in which to intervene to optimize engrafted islet mass.

Islets are damaged by inflammatory cytokines, which are expressed in the islet graft and upregulated in the TPIAT recipient immediately after surgery

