Cytokines are expressed from the islet graft itself, induced by the stress of isolation and transplant. Montolio et al demonstrated that TNF α and IL-1 were both highly upregulated in islet tissue immediately after isolation and following a one day culture period, and increased after transplantation into streptozotocin-induced diabetic Lewis rats (day 1, 3, and 7 post-transplant) even when conditions of normoglycemia were maintained (17). When islets are infused into the intraportal environment, islet expression of tissue factor triggers an instant blood mediated inflammatory reaction (IBMIR), in which the complement and coagulation cascades are activated. That, in turn, exacerbates the non-specific inflammatory response, leading to neutrophil and macrophage infiltration into the graft, increased local cytokine expression, and ultimately islet loss (23-26). Cytokines, particularly TNF α and IL1 β , are directly damaging to islets *in vitro* and are proposed to mediate similar damage *in vivo* post-transplantation (15, 16, 27, 28). Islet isolation itself induces high rates of beta cell apoptosis, due to the stress of

the isolation procedure, and this apoptosis is unfortunately exacerbated when islets are exposed post-isolation to TNF α (15). Thus, the immediate post-operative period is an opportunity for meaningful intervention.

Further contributing to a pro-inflammatory milieu is the major surgical procedure of total pancreatectomy and islet autotransplantation in patients with underlying history of chronic and/or recurrent acute pancreatitis. Multiple pro-inflammatory cytokine/ chemokine pathways are upregulated in the one week period following surgery in clinical TPIAT recipients (18). Itoh et al demonstrated that the “danger signal” high-mobility group box-1 (HMGB-1) was upregulated in islet grafts from clinical TPIAT recipients and that elevated HMGB-1 levels were directly correlated with greater post-transplant inflammation which in turn was negatively associated with islet graft outcomes, as measured by insulin independence (18). Pro-inflammatory cytokines are notably much following TPIAT with an adequate islet graft compared to pancreatectomy alone or TPIAT with very few islets, demonstrating that in fact this inflammatory response is elicited by the intraportal infusion of the islet graft and not simply a consequence of the major surgery (26).

Promisingly, therapeutic agents that target damaging inflammation are clinically available

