In addition to the metabolic data collected under this protocol, all TPIAT patients are enrolled in a prospective follow up study tracking diabetes, pain, and health related quality of life outcomes on an ongoing basis. Under this protocol, patients complete the SF-36 health related quality of life instrument and institutional derived questionnaires that include self-report of daily insulin use, pain symptoms, and pain medications. These instruments are administered at 3 months and 6 months after TPIAT and then once yearly after TPAIT. Copies of these instruments are included in the supplementary materials for reference. These assessments will permit long-term follow up of the study participants for both insulin requirements and health-related quality of life outcomes.

Design and Methods to Evaluate Specific Aim #3

SPECIFIC AIM #3: To evaluate the mechanistic effects of etanercept or alpha-1 antitrypsin on inflammation, islet cell viability/survival, and beta cell apoptosis. This will be assessed by repeated measurement of circulating cytokine and chemokine levels and circulating unmethylated DNA (a recently validated marker of beta cell death in T1DM) in patient serum during days 0 - 28.

Hypothesis 1: Peak levels and area under the curve for inflammatory cytokines will be lower in recipients treated with alpha-1 antitrypsin and etanercept.

Hypothesis 2: Lower rates of beta cell death will be observed post-transplant in the A1AT-treated and etanercept-treated groups, compared to standard of care, as evidenced by lower levels of circulating unmethylated insulin DNA in the patient serum.

To evaluate the potential mechanistic effects of the two drug therapies, we will obtain frequent serum measurements in recipients for critical markers including key cytokines/chemokines and markers of coagulation (the instant blood mediated inflammatory reaction), and markers of circulating exocrine tissue (trypsinogen). In addition, we will profile in each patient beta cell death(islet loss) using the novel marker for unmethylated insulin DNA. Unmethylated insulin DNA is specific to beta cells, and elevated levels in serum indicate beta cell death. Patient assessments are described in detail below.

1) Patient assessments:

- a. **Inflammatory Cytokines:** Patient serum will be assayed for TNF α , IL-1, IL-6, IL-8, IL-10, MCP-1, IP-10, and CCL2—at pre-surgical (x2 draws) and pre-infusion baseline, and at times 1, 3, 6, 12, 24,

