and 72 hours and 7 days after islet infusion. Assays will be performed using a Luminex ® multiplex bead cytokine kit. These measures were selected based on the literature suggesting relative importance in islet transplantation. These assessments are run in a CLIA certified cytokine laboratory (University of Minnesota cytokine laboratory).

In addition, thrombin-antithrombin complexes, C3a, and C-peptide will be obtained pre-infusion and at times 1, 3, and 24 hours post-transplant, as a marker of the instant blood mediated inflammatory response.

- b. Unmethylated insulin DNA: This novel marker has recently been validated as a measure of beta cell loss in new onset type 1 diabetes. Dying beta cells release unmethylated insulin DNA into the serum (43). The assay technique is performed as described by Herold et al (43). DNA is purified from 200 microliters of serum, using QIAamp DNA blood kits, and bisulfite treated using EZ DNA methylation kit. Unmethylated insulin DNA is measured by real-time PCR. Levels are elevated preoperatively and in new onset T1DM, but lowered when T1DM subjects are treated with teplizumab to preserve beta cell mass. Thus, we propose that this novel marker will provide critical mechanistic data on post-transplant loss of beta cell mass. This marker will be drawn prior to surgery and infusion (x 2 samples) and at 15 min, 30 min, 1, 3, 6, 12, 24, 72 hours, and 7, 14, and 28 days post-transplant, and repeated at each follow up visit (90 day, 1 year, 2 year).
- c. Alpha-1 antitrypsin levels: Measured at pre-treatment and prior to each infusion in the A1AT-treated group. In the control and etanercept groups, these levels will be measured at baseline and weekly through day 28 for comparison.
- d. Trypsin and Trypsinogen activated peptide (TAP): To determine if dying acinar cells release activated proteases which degrade the insulin molecules in systemic circulation, trypsin levels will be measured in the patient's serum pre- and at 12 and 24 hours post-islet infusion and by detection of TAP in the urine at 24 hours post-transplant by enzyme immunoassay (81). TAP is a small, measureable peptide that is released when trypsinogen is activated to trypsin.

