This is a pilot, parallel-arm study to compare etanercept, A1AT, and control groups; the primary outcome is maximal potentiated arginine induced insulin secretion (AIRmax) measured at 90 days posttransplant. We propose to enroll 15 patients in each group which will give 80% power to detect a difference between any two groups of at least 1.06*(within-group standard deviation of the outcome). From preliminary data for AIRmax measured more than one year post-transplant, the study will have 80% power to detect a difference of at least 33 mU/mL in pairwise comparisons of AIRmax between each of the 3 groups, corresponding to a 24% increase over standard treatment (control group).

The table below shows estimated minimum detectable differences for main outcomes, based on means and standard deviations from preliminary testing performed at 1 year post-transplant (for IVGTT and MMTT) or beyond 1 year post transplant (GPIAS) in this population of TPIAT recipients.

Test	Derived Measure	minimum detectable difference	n	Mean	SD
GPAIS	AIRmax (mU/mL)	33	10	137	31
IVGTT	AIRglu (mU/mL*min)	162	33	169	153
	ACRglu (ng/mL *min)	8.8	36	9.8	8.3
MMTT	AUC C-peptide (ng/mL *min)	147	39	295	139
	AUC glucose (mg/dL *min)	3790	39	16,037	3,579

For specific aim 1, the primary outcome, AIRmax, and other measurements at day 90 will be compared between treatment groups with a linear model to adjust for transplanted islet mass and the randomization stratum, BMI (< or \geq 27 kg/m²). For aim 2, the same analysis will be performed for measurements made at 1 year and 2 years post-transplant. In addition, we will assess whether day 90 AIRmax and AIRglu measurements predict insulin independence at 1 and 2 years post-transplant using a logistic regression model. For aim 3, repeated measurements during the weeks immediately post-transplant will be summarized by peak and area under the curve for comparison by the same linear model used for aim 1, i.e., adjusting for transplanted islet mass and the randomization stratum. We will also compare the groups based on the longitudinal series of measurements using a mixed-effects linear model with fixed effects of treatment group, transplanted islet mass and randomization stratum, and a random intercept for each participant to model the correlation between repeated measurements from the same person.

POTENTIAL RISKS AND BENEFITS

Forseeable Risks

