Unmethylated insulin DNA*			X	X	X		X	X	X		X	X	X
Serum trypsin and urine TAP*			X										
A1AT levels	X	X			X		X	X	X				
Liver injury markers*			X	X	X								
Study Drug Administration													
Etanercept (only for Etan. arm)		day 0		X	X	X	X	X					
A1AT (only in A1AT arm)		day -1		X	X		X	X	X				

* These mechanistic assessments during "transplant visit" include multiple draws. Please refer to text in protocol for specific times of draw.

Patients will be inpatient per usual clinical care through day 7 at minimum.

** +/-1 day window for labs and assessments. Study drug should be given on day 21 and day 28 whenever possible for consistency.

References

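### Minor: the supplementary Aim 3 mixed model lists no draw time and no treatment-by-time term, so it cannot show when the arms differ

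*Combined protocol and SAP*

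**What the plan says.** All passages are in the combined protocol and SAP.

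- **Lead Aim 3 analysis** (Sample Size and Plan for Data Analysis): "repeated measurements during the weeks immediately post-transplant will be summarized by peak and area under the curve", compared with the Aim 1 linear model.
- **Additional analysis** (same section): the longitudinal series is also compared with "a mixed-effects linear model with fixed effects of treatment group, transplanted islet mass and randomization stratum, and a random intercept for each participant". The list of terms ends there.
- **Cytokine draws** (Design and Methods to Evaluate Specific Aim #3): "pre-surgical (x2 draws) and pre-infusion baseline, and at times 1, 3, 6, 12, 24" and 72 hours, then day 7. That is seven post-infusion draws.
- **Insulin DNA draws** (same section): "15 min, 30 min, 1, 3, 6, 12, 24, 72 hours, and 7, 14, and 28 days post-transplant", which is eleven draws. In the visit schedule table before the References, the row "Unmethylated insulin DNA" is also marked at day 21, which makes twelve.
- **Timing of the biology** (Background): cytokine "pathways are upregulated in the one week period following surgery". For apoptosis, "High levels of beta cell apoptosis are observed, particularly in the 7 days after surgery, with apoptosis observed even at 30 days". In vitro and animal work describes apoptosis as "increasing over the first 10 days post-transplant".

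**The concern.** A longitudinal model is normally fitted to learn something that one summary per participant cannot give. Here the listed terms reduce the series to a single average in which every draw counts the same. The draws are packed into the first day, so that average leans on the first 24 hours for insulin DNA. An arm difference confined to part of the series would be reported as one diluted number with no sign of its timing.

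Two lesser consequences follow from having no time term at all. The rise and fall common to every participant is treated as noise. And an arm that misses draws near the surge looks lower for that reason alone.

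What is at stake is the reading of the mechanistic data. Objectives and Specific Aims says that these data, with day 90 graft function, will help select the agent, but it does not tie selection to this model.

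**Working it through.** **The plan's own figure.** No power is stated for this model. The only power statement is 80% for 1.06 SD with 15 per arm. A noncentral t with 28 df (two-sided 5% assumed) and noncentrality 1.06 x sqrt(15/2) = 2.90 gives 80.0%, so it reproduces.

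**1. What the coefficient estimates.** With the same complete draws for everyone, the random-intercept treatment coefficient equals the arm difference in unweighted participant means. A simulated check (45 participants, 11 draws, assumed parameters) gave the same value both ways to four decimals: -0.4752 for an early-only effect, -0.2198 for late-only and -1.0906 for constant. Adding a time main effect left all three estimates unchanged. Only treatment-by-time can show timing.

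**2. Weight of the first 24 hours, insulin DNA.** The average gives it 7/11 = 63.6%, or 7/12 = 58.3% with day 21. It covers 24/672 h = 3.6% of the 28 days, and these draws carry 7.1% of trapezoid time weight. The average and the AUC can therefore disagree.

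**3. Share of the full effect kept by the average** (mean of the effect profile over draws):

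| Effect profile | Share kept |
|---|---|
| Constant, either marker | 100% |
| Cytokines, whole week | 7/7 = 100% |
| Insulin DNA, through day 7 | 9/11 = 82%, or 9/12 = 75% |
| Insulin DNA, zero at infusion, linear to day 10, then flat (assumed) | 3.195/11 = 29%, or 4.195/12 = 35% |

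In the last row the nine draws to day 7 sum to 286.75 h, and 286.75/240 = 1.195. Each later draw adds 1. If a fraction s of the effect is already present at infusion, the 11-draw share is s + (1 - s) x 0.29. For s = 0.25, 0.5 and 0.75 this is 47%, 65% and 82%.

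**4. Power, for illustration only.** None of these inputs is in the documents: log scale, 15 per arm, between-participant and residual SD both 0.5, full effect 0.70, no covariates. For k draws, d = 0.70 x share / sqrt(0.25 + 0.25/k). With k = 11:

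- Constant effect: d = 1.34, power 94%. Windows do no better (93% up to 24 h, 91% from 72 h).
- Through day 7: d = 1.10, power 83%, against 93% for draws up to 24 h.
- Zero-start rise: d = 0.39, power 18%, against 70% for 72 h to day 28. With s = 0.25, 0.5 and 0.75 the average has 38%, 63% and 83%.
- The window figures are unadjusted. With Bonferroni for two windows, 93% becomes 88% and 70% becomes 59%.

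**5. Time left out, complete draws.** Take an assumed cytokine log surge of 1.5, 2.5, 2.2, 1.6, 1.0, 0.4, 0.1 over the seven draws. Its variance is 4.714/6 = 0.786, so the expected within-participant mean square without time is 0.25 + 0.786 = 1.04. At between-participant SD 0.3 the expected between-participant mean square is 7 x 0.09 + 0.25 = 0.88, which is smaller. The intercept variance is then often estimated as zero and the standard error is too large. Under three such surges, simulated type I error is about 2.5-3%. At SD 0.5 the between mean square is 7 x 0.25 + 0.25 = 2.0 and the change is negligible.

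**6. Time left out, unequal missed draws.** With no true effect, and the 6 h and 12 h draws missed in one arm only, simulation gives:

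- 2 of 15 participants: bias -0.02 to -0.04, type I error 4.3-5.5%.
- 5 of 15 participants: bias -0.06 to -0.11, type I error 5.7-8.0%.
- With categorical time: bias within 0.01, type I error 4.7-5.1%.

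**The case against.** The strongest reply is that the model answers the question asked. No Aim 3 hypothesis concerns when arms differ. The first names cytokine peak and AUC, and the second concerns lower insulin DNA levels. Peak and AUC lead the analysis, and an overall mean difference is a fair supplementary summary of lower levels. This stands, and it is why the point is minor. A time profile is a gain, not the repair of a broken test.

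A reader might infer from the 10-day statement in the Background that the average would keep only 29-35% of an insulin DNA effect. The documents do not support that. The figure needs an effect of zero at infusion, while the same Background reports high apoptosis from isolation itself and stresses the first 7 days. A drug that cut beta cell death by a constant fraction would give a roughly constant effect on the log scale, where the planned average does best.

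A reader might also infer that a time main effect matters only if draws are missed. That is true of the estimate but not of the test, as step 5 shows.

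Missed early draws are probably uncommon, because the schedule footnote keeps patients in hospital through at least day 7. The missing-draw bias is therefore a safeguard argument, not an expected problem.

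**Conclusion.** The point holds as a minor, inexpensive improvement. The stated model has no draw time and no treatment-by-time term, so with complete draws it returns one equal-weight average and cannot locate an arm difference in time. That conclusion and the draw counts need no assumption beyond complete data and the use of post-infusion draws to day 28 as outcomes.

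The size of any dilution is unknown. It is nil for a constant effect or a week-long cytokine effect. For an insulin DNA effect through day 7, 75-82% is kept. The 29-35% share is an assumed extreme, not the expected loss. All power, bias and type I error figures for this model rest on assumed SDs, effects and surge shapes, so they show direction rather than the loss in this trial.

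Nothing here touches the primary endpoint. It would also go too far to say that selection of the agent is compromised, since the plan does not base it on this model.

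**What to change.** - Add categorical draw time and treatment-by-time to the mixed model, keeping transplanted islet mass and BMI stratum.
- Report the all-draw average arm difference as the main result of this model. Add time-specific differences, or a few pre-specified windows (for example up to 24 h and, for insulin DNA, 72 h to day 28), labelled exploratory.
- If the interaction is tested, let correlation fall with the time gap or use a Greenhouse-Geisser type correction. With a random intercept only, simulated type I error was 7.5-9.0% at a correlation of 0.6 between adjacent draws, against 4.0-4.4% with the correction.
- Keep peak and AUC first.
- Reconcile the day 21 insulin DNA draw between the Aim 3 methods and the visit schedule table. The Study Flowchart groups days 7 to 28 in one column and defers to the methods, so it does not settle the matter.

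**Cost.** No new samples, only plan wording and some within-participant degrees of freedom. For three arms and seven cytokine draws these are 6 for time and 2 x 6 = 12 for the interaction, out of 45 x 7 = 315 values. The main cost is multiplicity: 8 listed cytokines x 7 draws x 3 pairs = 168 exploratory contrasts without error control. Windows can also lose power when an effect persists. For an assumed cytokine effect from 3 h to day 7, the 24 h window has 77% power against 84-85% for the average, which is why the average should stay in front.
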